6.7 BASELINE, TIME WINDOWS AND CALCULATED VISITS

The table below presents the visit structure according to the study flowchart depending on the time window scheduled in the CTP.

Table 6.7: 1 Visit structure

Period	Baseline	Trial drug admin.	On-treatment & Post-treatment					
Visit number per protocol	V1A		V1B#	V1C#	V2	V3	V4	V5
Planned study window	-4.5-0 hour	↔x→ 60 mins	1 hour ± 15 mins	2 hrs ± 30 mins	24 hrs ± 2hr	7 days ± 3 day	30 days ± 3 days	90 days ± 7 days
Study Day	← D0 →			D1	D7	D30	D90	
Visit description*	Baseline		Day0 (1H)	Day0 (2 H)	Day1	Day7	Day30	Day90

*label to be used in tables.

‘Baseline’ is defined as from enrolled in this study to the start time of bolus treatment administration

‘Study Day’ is calculated from the date & time of starting bolus treatment administration.

date & time is calculated from the date & time of starting infusion treatment administration.

Start of treatment:

The start of treatment (used for survival start time, length of stay in hospital, treatment at onset for adverse event) will be the **start of bolus treatment administration**; end of treatment is the end of infusion/drug/treatment administration.

Baseline value:

The baseline value will be the value recorded at V1A (last available value before the start of bolus treatment).

Change from baseline:

The change from baseline for any efficacy or safety endpoints (Vital signs) will be calculated as: value after baseline – value at baseline (V1A).

All efficacy analyses will be based on ‘nominal visits’ (CRF raw data visit) which will be labelled as indicated in the ‘Visit description’ row in tables, listings and graphs.

7. PLANNED ANALYSIS

Unless otherwise specified, the following general conventions for End-of-Text (EoT) [\[5\]](#) tables should be used regarding all descriptive statistical analysis and result presentations.

The set of summary statistics: N / Mean / SD / Min / Median / Max are for continuous data with one more decimal place compared to the original data in the subject data listing. For tables that are provided for endpoints with some extreme data, Q1 and Q3 would be preferred to Min and Max.

Tabulations of frequencies for categorical data will include all possible categories and will display the number of observations in a category as well as the percentage (%) (unless otherwise specified, all patients in the respective patient set whether they have non-missing values or not). Percentages will be rounded to one decimal place. The category missing will be displayed only if there are actually missing values. All the confidence interval calculations for proportions will use the Wilson score method.

The visit will be analysed as calculated visit and should be named ‘Baseline’, ‘Day0(1H)’, ‘Day0(2H)’, ‘Day1’, ‘Day7’, ‘Day30’ and ‘Day90’ as described in [Section 6.7](#). The units of variables should be given in the titles or column/row descriptors in square brackets (e.g. [mmHg]), unless the variable does not have a unit (e.g. scores). And the imputation rules for missing data will be applied as in [Section 6.6](#).

An independent data monitoring committee (DMC) will oversee the trial conduct, monitor safety data monthly, and review the interim analysis results when 60 patients complete the study. As for details please refer to DMC SAP. [\[6\]](#)

7.1 DEMOGRAPHIC AND OTHER BASELINE CHARACTERISTICS

Only descriptive statistics are planned for this section of the report.

7.2 CONCOMITANT DISEASES AND MEDICATION

Only descriptive statistics of concomitant therapy (medication and other treatment) are planned for this section of the report based on TS.

Concomitant therapy will be coded according to the WHO-DD (current version at the time of analysis), sorted by the ATC3 class and the preferred name (PN). PNs that belong to different ATC3 classes will be shown under all applicable ATC3 classes.

All concomitant therapies after the start of bolus until Visit 5 will be summarized. Antithrombotic therapies (e.g. aspirin, heparin, etc.) within 24 hours after the start of bolus will be summarized separately.

Concomitant therapy without end date will be considered as ongoing.

7.3 TREATMENT COMPLIANCE

Not applicable.

7.4 PRIMARY ENDPOINT(S)

Primary analysis

The primary efficacy endpoint is the percentage of mRS 0-1 (favourable outcome) responder at Visit 5 after stroke onset by face-to-face interview with patient. The proportion of patients with mRS 0-1 will be presented with corresponding 95% confidence intervals (CIs). The imputation rules described in [Section 6.6](#) will be applied for the primary analysis. The observed case analysis, that is the proportion of patients with mRS 0-1 observed at Visit 5, will be performed as sensitivity analysis.

The null hypothesis of $p \leq 40\%$ versus the alternative hypothesis of $p > 40\%$ will be tested using a one sample t-test at two-sided significance level of 0.05. The horizontal stacked bar graphs of each level in the ordinal mRS will be presented.

The primary safety endpoint is the proportion of patients with symptomatic intracranial haemorrhage (sICH) evaluated by DMC consultants within whole study period. The proportion of patients with sICH will also be presented along with corresponding 95% CIs.

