### **7.2 NULL AND ALTERNATIVE HYPOTHESES**

Alteplase (rt-PA) has been approved and widely used in more than 100 countries for about 20 years. Many studies were conducted by the sponsors and researchers to understand the efficacy and safety profiles of the drug for patients treated within 3-4.5 hours after AIS onset in both controlled clinical studies and real world setting. The percentage of mRS 0-1 responder at day 90 was 40.9% in SITS-ISTR [[P15-11922](#)] 52.4% in ECASS III (ITT population) and 60.9% in TIMS-China [[P13-12586](#)]. The estimation from historical review varies from 40% to 60%.

In this study, we are aiming to rule out a response rate of 40% or lower, which is considered as insufficient level of efficacy for alteplase treated within 3-4.5 hrs from stroke onset in Chinese acute ischemic stroke patients [[P13-12586](#)]. Therefore, a null hypothesis of  $p \leq 40\%$  versus an alternative hypothesis of  $p > 40\%$  will be tested using a one sample test at two-sided significance level of 0.05, where  $p$  denotes the response rate in Chinese patients who are treated within 3-4.5 hrs after stroke onset.

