## 7.7 DETERMINATION OF SAMPLE SIZE

The study will enrol approximately 120 patients. The sample size calculation takes account into both safety and efficacy considerations.

Regarding the primary safety endpoint, an observed sICH rate of 2.4%, i.e., 3 sICH events out of 120 patients, will result in an exact binomial 95% CI (0.48%, 6.99%) with the confidence width as 6.51%, which is considered as reasonable estimation precision.

The percentage of mRS 0-1 (favourable outcome) responder at day 90 is the primary efficacy endpoint. The range of the response rate from historical review was from 40% to 60% [P05-03664]. If assuming an underlying response rate of 55% of rt-PA treatment in Chinese patients, for the planned sample size of 120 patients, a power of 91.5% can be achieved. The sample size calculations in Table 7.7.1 have been performed based on a one sample test for proportion with a two-sided significance level of 0.05 and power ranging from 80% to 90%. Calculations were performed using ADDPLAN version 6.

Table 7.7:1

Sample size calculations based on a one sample test with a two-sided significance level of 0.05 and various assumptions of percentages of mRS 0-1 responders (n=120)

Assumed mRS response rate	Number of mRS 0-1 responders	Power(%)
52.5%	63	79.4
53.3%	64	84.2
55.0%	66	91.5

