4. CHANGES IN THE PLANNED ANALYSIS OF THE STUDY

There has been no change in the planned analyses from the statistical methods described in the CTP.

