5.1 PRIMARY ENDPOINT(S)

The primary efficacy endpoint is the percentage of patients with mRS 0-1 (favourable outcome) at Visit 5 (i.e., Day 90) after stroke onset by face-to-face interview with patient. A patient is considered to be a mRS 0-1 responder (response value set to 1) if he/she obtained a response of 0 or 1 on the modified Rankin scale otherwise the response value will be set to 0.

The primary safety endpoint is the percentage of patients with symptomatic intracranial haemorrhage (sICH) centrally evaluated by DMC consultants according to ECASS III definition within the whole study period. ECASSIII definition is any apparently extravascular blood in the brain or within the cranium that was associated with clinical deterioration (defined by an increase in the National Institute of Health Stroke Scale (NIHSS) score of 4 or more points), or that led to death and that was identified as the predominant cause of the neurological deterioration.

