6.3 PATIENT SETS ANALYSED

The treated set (TS) includes all enrolled patients who received alteplase (rt-PA) treatment at any dose. The full analysis set (FAS) is the same as TS since all treated patients will be evaluated.

All safety and efficacy analysis will be performed on the TS.

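### SAP 7.4 names a one-sample t-test for the 1/0 primary endpoint, while the power and the Wilson interval rest on a one-sample proportion test

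*SAP*

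**What the plan says.** - **Endpoint.** SAP 5.1 codes a patient with mRS 0 or 1 as a responder ("response value set to 1") and everyone else as 0.
- **Test in the SAP.** Section 7.4 states that the null of 40% or lower "will be tested using a one sample t-test at two-sided significance level of 0.05".
- **Test in the protocol.** Section 7.2 has the same sentence without the t: the hypothesis "will be tested using a one sample test at two-sided significance level of 0.05".
- **Power.** Protocol 7.7 says its calculations are "based on a one sample test for proportion with a two-sided significance level of 0.05". Table 7.7:1 gives 79.4%, 84.2% and 91.5% at assumed rates of 52.5%, 53.3% and 55.0% with n = 120.
- **Interval.** SAP 7: "All the confidence interval calculations for proportions will use the Wilson score method".
- **Sample size and analysis set.** Protocol 7.7: "The study will enrol approximately 120 patients". SAP 6.3: "All safety and efficacy analysis will be performed on the TS", meaning everyone who received any dose.
- **Declared changes.** SAP 4: "There has been no change in the planned analyses".

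**The concern.** The trial has one efficacy hypothesis. As the SAP is written, its p-value comes from a t-test, which uses the sample variance and a t reference. Its confidence interval comes from the score test, which uses the variance under the null. The power was also computed for a proportion test. The extra "t-" may be only a slip, but a programmer will code what SAP 7.4 says.

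If the two methods disagreed at the final count, the report would show a 95% CI excluding 40% beside p > 0.05. Neither document says which would then prevail: protocol 7.1 puts the weight on estimates with intervals, and protocol 7.2 specifies a test. The call would be made after seeing the data.

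**Working it through.** **Inputs.** Null rate p0 = 0.40 (protocol 7.2); assumed rates p1 = 0.525, 64/120 and 0.55, n = 120 and two-sided 0.05 (protocol 7.7); t-test (SAP 7.4); Wilson interval (SAP 7).

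**1. Reproduce the stated power.** Protocol 7.7 does not state the variance used. With the null variance, the score-test formula is

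power = Phi{ [p1 - p0 - 1.96 sqrt(p0(1-p0)/n)] / sqrt(p1(1-p1)/n) }.

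At p1 = 0.55: sqrt(0.24/120) = 0.04472, times 1.96 = 0.08765; sqrt(0.2475/120) = 0.04542; (0.15 - 0.08765)/0.04542 = 1.373; Phi = 0.915.

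| Assumed rate | Table 7.7:1 | Score formula | Noncentral t, variance p1(1-p1) |
|---|---|---|---|
| 52.5% | 79.4% | 79.4% | 77.6% |
| 53.3% (64/120) | 84.2% | 84.2% | 82.7% |
| 55.0% | 91.5% | 91.5% | 90.6% |

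The score formula matches all three rows to the printed decimal and the t formula matches none. That the score test was used is inferred from this match.

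**2. Why the two tests differ.** The Wilson lower limit exceeds 40% exactly when (phat - 0.4)/sqrt(0.24/n) > 1.96, which is the score test. The t-test divides by sqrt(phat(1-phat)/(n-1)) instead and uses a critical value of about 1.98. For phat between 0.4 and 0.6, phat(1-phat) is above 0.24, so near the upper decision boundary the t-test is slightly stricter.

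**3. At n = 120.**

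- 59 responders, phat = 0.4917. Score: 0.0917/0.04472 = 2.050, p = 0.040. t-test: standard error sqrt(0.24993/119) = 0.04583, t = 2.000, p = 0.048. Wilson interval 40.4% to 58.0%.
- 58 responders. Score p = 0.062, t-test p = 0.071, Wilson lower limit 39.6%.

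All three rules first succeed at 59. Exact upper-tail error is P(X >= 59 | 0.40) = 0.0260 and exact power is P(X >= 59 | 0.55) = 0.9153, whichever test is used.

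**4. At nearby sizes.** For each n from 110 to 130 (an assumed range), the smallest successful count above 40% was found under each rule. The rules differ at eight of the 21 sizes, always by one responder, with the t-test the stricter.

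| n | Conflicting count | Wilson lower limit | t-test p | Exact upper-tail error, score / t | Exact power at 55%, score / t |
|---|---|---|---|---|---|
| 112 | 55 | 40.03% | 0.0575 | 0.0315 / 0.0203 | 0.9110 / 0.8765 |
| 114 | 56 | 40.13% | 0.0549 | 0.0300 / 0.0193 | 0.9121 / 0.8783 |
| 116 | 57 | 40.21% | 0.0524 | 0.0286 / 0.0184 | 0.9132 / 0.8800 |
| 118 | 58 | 40.30% | 0.05002 | 0.0273 / 0.0176 | 0.9143 / 0.8817 |
| 121 | 59 | 40.03% | 0.0572 | 0.0313 / 0.0204 | 0.9290 / 0.9009 |
| 123 | 60 | 40.12% | 0.0547 | 0.0298 / 0.0195 | 0.9299 / 0.9022 |
| 125 | 61 | 40.20% | 0.0522 | 0.0284 / 0.0186 | 0.9307 / 0.9035 |
| 130 | 63 | 40.04% | 0.0567 | 0.0309 / 0.0205 | 0.9434 / 0.9205 |

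At these sizes the chance of observing the conflicting count is 2.3-3.4% if the true rate is 55%, 6.6-7.4% if 50%, and about 1% if 40%.

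**5. After the change.** The score test and the Wilson interval gave the same cut-off at every n from 50 to 160. An exact binomial test with at most 0.025 in the upper tail needs 60 of 120: P(X >= 60 | 0.40) = 0.0167 and P(X >= 60 | 0.55) = 0.8833.

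**The case against.** Five points can be made for leaving the text alone.

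- **Nothing changes at the planned size.** True: at n = 120 the decision, error and power are identical.
- **A conflict is unlikely.** The range 110-130 is not in the documents, and protocol 7.4 speaks of enrolment up to 120, which would leave only the four conflicting sizes below 120. Missing mRS is imputed, so drop-out after treatment does not change the primary n. If all 21 sizes were equally likely (an assumption), the overall chance of a conflict would be 8/21 of 2.3-3.4%, about 0.9-1.3%, at a true rate of 55%. This stands. The observed-case sensitivity analysis can, however, have a smaller n, and conflicts also occur at 103, 105 and 107.
- **The t-test is the safer test where they differ.** At all eight sizes its exact error is 1.8-2.1% against 2.7-3.2% for the score test, so its cut-off there is also that of the exact binomial test. This stands as a caution about the replacement. It does not make the t-test an exact test: at n = 120 it also succeeds at 59, with error 0.0260.
- **The SAP may be elaborating the protocol.** Protocol 7.2 leaves the type of one-sample test open, so the no-change statement in SAP 4 is only weakly contradicted. The clearer mismatches are with protocol 7.7 and with the Wilson interval.
- **A t-test on 1/0 data is not invalid at this size.** Agreed. The objection is that it does not match the interval or the power.

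**Conclusion.** The concern holds, at low severity. SAP 7.4 names a test that differs from the one behind the stated power and from the one the prescribed interval inverts. The stated 91.5% is not wrong, and at n = 120 only the printed p-value changes. At some other sizes a single responder count would give a p-value and an interval that point in opposite directions, with no rule to settle it.

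This rests on two assumptions: that the power calculation used the null variance, inferred from the match with Table 7.7:1, and that the final treated number may differ from 120, with 110-130 as an illustrative range.

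**What to change.** In SAP 7.4, replace the t-test with a one-sample score test for a proportion, null variance 0.4 x 0.6. The p-value, the Wilson interval and the protocol 7.7 power then come from one test at every n. State the drawback beside it: exact upper-tail error is 0.026 at n = 120 and up to 0.032 at the eight sizes above. The cost is one sentence and one line of code.

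If the sponsor prefers strict error control, name the exact binomial test instead. State that it needs at least 60 of 120 responders (exact upper-tail error 0.0167), give the power at 55% as 88.3% in place of 91.5%, and report an exact interval for this endpoint so that interval and test agree. This also means updating the power figure and the interval method for this endpoint.

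Either choice should be fixed before the outcome data are seen.

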7.5 SECONDARY ENDPOINT(S)

7.5.1 Key secondary endpoint(s)

Not applicable.

7.5.2 (Other) Secondary endpoint(s)

The secondary efficacy endpoint is the percentage of global outcome at Visit 5. A global outcome responder is defined as patient with outcomes at Visit 5 of a score of 0 or 1 on the mRS, a score of 95 or higher on the Barthel Index, a score of 0 or 1 on the NIHSS, and a

score of 1 on the Glasgow Outcome Scale. The proportion of global outcome responders will be displayed along with corresponding 95% CIs. Each item of the composite criteria global outcome responder (refer to [Section 5.2.2](#)) will be evaluated separately as well. Its observed result will also be summarized. The imputation rules described in [Section 6.6](#) will be applied for the primary analysis.

The secondary safety endpoints are:

- Patient's survival at Day 90 (censoring at 90 days)

The cumulative probability (Kaplan-Meier estimate) of death from bolus treatment administration to Day 90 will be analysed and plotted by a Kaplan-Meier survival with the median survival along with 95% confidence interval, using Greenwood's standard error estimate. The Kaplan-Meier estimates will also be analysed over the observation period of 90 days.

- Frequency of deaths related to stroke or of neurological causes will be analysed descriptively.
- Incidence of cerebral herniation and symptomatic edema will be analyzed descriptively.
- Frequency and severity of adverse events refer to [Section 7.8.1](#).

7.7 EXTENT OF EXPOSURE

Only descriptive statistics are planned for this section of the report.

7.8 SAFETY ANALYSIS

All safety analyses will be performed on the treated set (TS).

7.8.1 Adverse events

Unless otherwise specified, the analyses of adverse events (AEs) will be descriptive in nature. All analyses of AEs will be based on the number of patients with AEs and NOT on the number of AEs.

Multiple AE occurrence data on the CRF will be collapsed into an AE provided that all of the following applies:

- All AE attributes are identical (LLT, intensity, action taken, therapy required, seriousness, reason for seriousness, relationship, and outcome).
- The occurrences were time-overlapping or time-adjacent (time-adjacency of 2 occurrences is given if the second occurrence started on the same day or on the day after the end of the first occurrence).

For further details on summarization of AE data, please refer to the guidance [\[3, 4\]](#).

The primary interest analysis of AEs will be based on the concept of treatment emergent (on-treatment period) AEs, i.e. AEs which occurred through the single dose treatment phase and throughout the REP (i.e. exactly day 7). AEs stopped before the start of bolus treatment administration will be assigned to ‘screening’ and AEs occurring after the end of REP to Visit 5 will be assigned to ‘post-treatment’. The frequency of all AEs collected after Visit 5 until the end of the study (i.e. Visit5) defined as ‘post study’ will also be summarized. For details on the treatment definition, see [Section 6.1](#).

According to ICH E3 [\[7\]](#), AEs classified as ‘other significant’ needs to be reported and will include those non-serious and non-significant AEs with

- (i) ‘action taken = discontinuation’ or ‘action taken = reduced’, or

(ii) marked haematological and other lab abnormalities or lead to significant concomitant therapy as identified by the Clinical Monitor/Investigator at a Medical Quality Review Meeting.

An overall summary of AEs will be presented.

The frequency of patients with AEs will be summarised by primary system organ class (SOC) and preferred term (PT) of MedDRA (using the version that is current at the time of analysis). Frequency tables will be created for the following AEs:

- All AEs
- Serious AEs
- Drug-related AEs
- AEs leading to treatment discontinuation
- AEs leading to death
- Other significant AEs (according to ICH E3) [\[7\]](#)
- AEs with incidence in preferred term greater than 2%

The system organ classes will be sorted alphabetically, and preferred terms will be sorted by descending frequency within system organ class.

The above tables will be repeated within the on-treatment period and the overall period from Inform consent to Visit 5.

7.8.2 Laboratory data

Laboratory data will not be analysed. Any clinical significant abnormalities in laboratory will be reported as AEs.

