### **5.3.4 Safety laboratory parameters**

An abbreviated hematology and chemistry panel including liver and renal function testing will be analysed for safety at specific time-points throughout the trial by a certified laboratory. The laboratory tests will include:

Category	Laboratory test
Haematology	Red blood cell count (RBC) Haemoglobin (Hb) Haematocrit (HCT) Mean corpuscular volume White blood cell count including differential Platelet count
Biochemistry	Aspartate aminotransferase (AST) Alanine transaminase (ALT) Gamma-glutamyl trasferase (GGT) Alkaline phosphatase (ALP) Total bilirubin

	Creatinine Glucose Uric acid (optional) β- Human Chorionic Gonadotropin(HCG)*
Electrolytes	Sodium Potassium Calcium Inorganic phosphorus
Coagulation	International normalized ratio (INR) Partial thromboplastin time (ptt) Prothrombin time (PT)
Urinalysis	pH, glucose, erythrocytes, leukocytes, protein, nitrite (semi quantitative measurements; (-, +, ++, +++), pregnancy test*

Both of the two types of pregnancy tests are acceptable for this trial, whatever test it may be, it should be carried out appropriately, according to the routine practice of local lab of selected sites.

Note: for the urgent indication, if patient could not provide urine at the time point of screening for the routine urine test, investigator should judge, according to the baseline condition of the patients, to decide whether the missing data of routine urine test will impact patients' participate in the clinical trial. Urine test should be conducted at the earliest time when it is available afterwards for safety consideration.

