### **6.2.3      Observation Period and Trial Completion**

A physical examination, the documentation of adverse events and of concomitant medication will be performed for all patients at all predefined treatment time points (Visit 1B and Visit 1C) as of the administration day and visit 2,3,4, and 5.

Lab test at visit 1A and visit 3 are mandatory. It will be optional at visit 2 and visit 5 in case of clinical deterioration (considered by investigator)

At visit 1B (i.e., 1 hour after the start of infusion of study drug), vital signs will be measured every 30 minutes until Hour 2. An 12-lead ECG recording will be made.

At visit 1C (i.e., 2 hours after the start of infusion of study drug), the NIH Stroke Scale will be performed. Vital signs will be measured every 30 minutes for 6 hours, then hourly until 24 hours. An 12-lead An 12-lead ECG recording will be made.

At visit 2 (24 hours), vital signs will be measured. The NIH Stroke Scale will be performed. A second imaging (CT/MRI) scan will be done within Hour 22 and Hour 36 after start of infusion of study drug.

At visit 3 (on day 7), vital signs will be measured. The NIH Stroke Scale will be performed. An 12-lead ECG recording will be made. A CT/MRI scan will be performed in case of clinical deterioration

At visit 4 (on day 30), vital sign will be measured. The NIH Stroke Scale, the modified Rankin Scale, and the Barthel Index will be performed. A CT/MRI scan will be performed in case of clinical deterioration.

At visit 5 (on day 90), vital sign will be measured. The NIH Stroke Scale, the Glasgow Outcome Score, the modified Rankin Scale, and the Barthel Index will be performed. A physical examination takes place. The patient termination record will be filled in. Length of stay in hospital will be assessed as well.

The trial completion (end of the trial) eCRF page has to be filled-in when patient has terminated the trial.

The end of the trial is:

- At the end of visit 5(Day 90 per protocol) for patients who have completed the trial on treatment and came to future visits as planned.
- After early discontinuation, if a patient refuses to attend future visits as originally planned.

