### **7.3.4 Safety analyses**

Safety analysis will be performed based on full analysis set.

Patient's survival at Day 90 (censoring at 90 days) will be analysed using the Kaplan-Meier method. The median survival along with 95% confidence interval, using Greenwood's standard error estimate, will be presented. The Kaplan-Meier estimates will also be plotted over the observation period of 90 days.

The frequency of death related to stroke or of neurological causes and the incidence of cerebral herniation and symptomatic edema will be analysed descriptively.

Adverse events will be coded using the Medical Dictionary for Regulatory Activities (MedDRA) coding dictionary. The frequency, severity and causal relationship of adverse events will be tabulated by system organ class and preferred term after coding according to MedDRA. Because this study is a single dose drug administration (duration of approximately one hour), the incidence and severity of adverse events will be displayed by treatment periods. All AEs which occurred through the single dose treatment phase and throughout the REP will be considered as on treatment. Events which occurred after the REP will be considered as post treatment. The frequency of on-treatment AEs will be summarized as primary interest. The frequency of all AEs collected until the end of the study will also be summarized. More

details will be specified in Statistical Analysis Plan. Standard BI summary tables and listings will be produced.

Vital signs, physical examinations, or other safety-relevant data observed at screening, baseline, during the course of the trial and at the end-of-trial evaluation will be assessed with regard to possible changes compared to findings before start of treatment.

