## **Haemorrhage**

The most frequent adverse reaction associated with Actilyse is bleeding in different forms resulting in a fall in haematocrit and/or haemoglobin values.

very common	intracerebral haemorrhage represents the major adverse reaction in the treatment of acute ischaemic stroke (up to 15 % of patients without any increase of overall mortality and without any relevant increase in overall mortality and severe disability combined, i.e. mRS of 5 and 6).  bleeding from damaged blood vessels (such as haematoma)
common	intracerebral haemorrhage (such as cerebral haemorrhage, cerebral haematoma, haemorrhagic stroke, haemorrhagic transformation of stroke, intracranial haematoma, subarachnoid haemorrhage) in the treatment of acute myocardial infarction and acute pulmonary embolism  pharyngeal haemorrhage  gastrointestinal haemorrhage (such as gastric haemorrhage, gastric ulcer haemorrhage, rectal haemorrhage, haematemesis, melaena, mouth haemorrhage, gingival bleeding)
	ecchymosis  urogenital haemorrhage (such as haematuria, haemorrhage urinary tract)  injection site haemorrhage (puncture site haemorrhage, catheter site haematoma, catheter site haemorrhage)
uncommon	pulmonary haemorrhage (such as haemoptysis, hemothorax, respiratory tract haemorrhage)  epistaxis  ear haemorrhage
rare	eye haemorrhage  pericardial haemorrhage  retroperitoneal bleeding (such as retroperitoneal haematoma)
not known***	bleeding in parenchymatous organs (such as hepatic haemorrhage)

Death and permanent disability are reported in patients who have experienced stroke (including intracranial bleeding) and other serious bleeding episodes.

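### SAP 7.8.2 leaves all laboratory data out of the analysis, although the protocol collects them as mandatory safety parameters and, on its natural reading, commits to assessing their change from before treatment

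*SAP*

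**What the plan says.** - SAP 7.8.2 (Laboratory data): "Laboratory data will not be analysed". The only substitute is that "Any clinical significant abnormalities in laboratory will be reported as AEs".
- Protocol 7.3.4 (Safety analyses) makes a commitment that runs from screening through to the final evaluation. The data it covers are not confined to vital signs and physical examinations; a general class of safety-relevant data is added. What it undertakes is that these "will be assessed with regard to possible changes compared to findings before start of treatment".
- Protocol 5.3.4, the section on safety laboratory tests, says of them: "An abbreviated hematology and chemistry panel including liver and renal function testing will be analysed for safety at specific time-points throughout the trial". The table there lists haemoglobin, haematocrit, platelets, INR, PTT and PT, among others.
- Protocol 6.2.3: "Lab test at visit 1A and visit 3 are mandatory".
- Protocol appendix 10.6, under Haemorrhage, says that the most frequent adverse reaction to the product is "bleeding in different forms resulting in a fall in haematocrit and/or haemoglobin values".
- SAP 4: "There has been no change in the planned analyses from the statistical methods described in the CTP".

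**The concern.** The protocol requires a laboratory panel before treatment and about a week later, in a trial whose objective covers safety as well as efficacy. The SAP then excludes every laboratory value from analysis without listing this as a departure. What reaches the report is what someone judged important enough to record as an AE. A moderate fall in haemoglobin or platelets across many patients, each below that threshold, would appear in no planned table. The point has some weight here because the label text in appendix 10.6 ties the product's most frequent reaction to falls in haematocrit or haemoglobin. What is at stake is the completeness of the safety description, not a primary or secondary endpoint result.

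**Working it through.** The plan gives no figure to reproduce, so the check sets the texts side by side.

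1. **Are laboratory data within the protocol's commitment?** The sentence in protocol 7.3.4 names vital signs and physical examinations, then adds a general class of safety-relevant data. It does not name laboratory data. Protocol 5.3.4, which sits in the section on assessment of safety, calls the tests safety parameters, so it is natural to place them in that class. Protocol 5.3.4 also says that the panel is analysed for safety, but by a certified laboratory, which most naturally means assayed. The argument therefore rests on 7.3.4, with 5.3.4 used only to classify the data.

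2. **Do paired values exist?** Protocol 6.2.3 makes the tests mandatory at Visit 1A and Visit 3. With 120 patients planned, the ceiling is 120 pairs, or 2 × 120 = 240 panels. Deaths, withdrawals and missed Visit 3 attendances lower it. Flow Chart footnote 5 says which results must be known before dosing; for the others, this is recommended only. It governs when results are available and does not cancel the Visit 1A panel. SAP 6.7 defines baseline as the last value before the bolus, so a sample drawn after the bolus would not count, and a table should report the number of pairs.

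3. **Is the timing useful?** Visit 3 is day 7 ± 3 (protocol 6.3.1), so days 4 to 10. The on-treatment period for AEs ends 7 days after dosing (protocol 5.3.7.2, SAP 6.1). The pair therefore spans most or all of the period of primary safety interest.

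4. **What does the SAP provide instead?**
   - Change from baseline for safety data is defined in SAP 6.7 with vital signs as the only named item, and SAP 7.8.3 tabulates them.
   - Laboratory changes become AEs only if the investigator judges them clinically relevant (protocol 5.3.7.2; SAP 7.8.2 is to the same effect).
   - SAP 7.8.1 has a category of other significant AEs that can take in marked laboratory abnormalities. The Clinical Monitor or investigator identifies them at a quality review meeting, and they get a frequency table.

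5. **Does item 4 deliver item 1?** The AE routes count judged events. They give no mean or median change, no spread, and no count of patients moving from normal to low. The other-significant category draws on events already recorded as AEs, so it does not screen the laboratory data.

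6. **Is the omission declared?** SAP 4 says that nothing has changed. SAP 7.8.2 is an explicit exclusion, not detail left to be filled in.

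**The case against.** The strongest reply is that the protocol never promises a laboratory table. Its sentence speaks of assessment, not summary statistics. Protocol 5.3.7.2 describes how clinically relevant changes in vital signs, ECG, physical examination and laboratory results become AEs. SAP 7.8.2 follows that route for laboratory data, as SAP 7.8.4 does for ECG. Physical examinations, which 7.3.4 does name, also have no SAP section. On this reading SAP 4 is accurate.

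Part of this stands. Laboratory data are not named, and a reader who inferred an explicit promise of change-from-baseline laboratory tables would be going beyond the text. But vital signs take the same AE route in protocol 5.3.7.2 and the SAP still tabulates them, so AE reporting is not treated as a full substitute for assessing change.

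A reader might also infer that laboratory safety rests solely on the investigator, or that these values would never be seen. Neither is supported. Sites review results, SAP 7.8.1 offers the other-significant category, and SAP 7 has the data monitoring committee (DMC) monitor safety data monthly, although the DMC SAP is not among the documents and its laboratory coverage is unknown.

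Nor does the omission leave bleeding unexamined. For stroke, appendix 10.6 names intracerebral haemorrhage as the major reaction. Symptomatic intracranial haemorrhage is the primary safety endpoint and is evaluated centrally. Other bleeding is collected as AEs to Day 90 and tabulated. The haemoglobin sentence is label text covering several indications and describes the fall as a result of bleeding.

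Finally, with no control arm, a change by Visit 3 could not be attributed to alteplase. That limits interpretation; it does not make a descriptive summary pointless.

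**Conclusion.** The point holds as a minor gap in safety reporting. SAP 7.8.2 excludes data that the protocol classes as safety parameters, requires at two visits and, on the natural reading of 7.3.4, commits to assessing for change, while SAP 4 declares no change. The AE routes soften the gap without closing it, because they depend on judgement and show neither the distribution of change nor shifts out of range.

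In size, at most 120 paired sets of values go unsummarised. The documents give no basis for estimating any change that would be missed. Laboratory values are neither a primary nor a secondary endpoint in their own right, so the mRS and sICH results do not move.

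The conclusion assumes that the general wording in protocol 7.3.4 covers the tests in 5.3.4, and that the Visit 1A and Visit 3 panels are done as required. If the first assumption is rejected, the charge of an undeclared departure weakens, but the case for a descriptive table remains.

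**What to change.** Replace SAP 7.8.2 with the following, in patients with both a Visit 1A and a Visit 3 value, stating the number of pairs for each test:

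- Haemoglobin, haematocrit and platelets: descriptive statistics at each visit and for the change, plus the number and percentage moving from normal to below normal.
- Coagulation tests (INR, PTT, PT): the same statistics, plus the number and percentage moving from within to outside the normal range.
- Shifts judged against each laboratory's own reference range.

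Keep the AE and other-significant AE tables, and label the new tables descriptive, with no test.

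The cost is one or two standard tables from data already required, with no new procedures. The real work is collecting and applying local reference ranges and, for the change summaries, checking units across about 15 sites. Recording the omission in SAP 4 would correct that statement but would not supply the missing information, so it is not enough alone.
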